### **Hepatic Laboratory Abnormalities of Interest**

Among the events assessed under "Assessment of Hepatic Laboratory Values," the following criteria are of interest:

- Confirmed post-nadir ALT  $> 5 \times$  ULN;
- Post-nadir ALT  $> 3 \times$  ULN and a concurrent total bilirubin  $> 2 \times$  ULN with a direct bilirubin:total bilirubin ratio  $> 0.4$ .

To support the assessment of hepatic laboratory abnormalities of interest, the following potential events will be summarized:

- Confirmed post-nadir ALT  $> 5 \times$  ULN;
- Post-nadir ALT  $> 3 \times$  ULN and total bilirubin  $> 2 \times$  ULN and direct/total bilirubin ratio  $> 0.4$ .

Two listings (one for each bullet) of all liver function tests including ALT, AST, total, indirect and direct bilirubin, ratio of direct to total bilirubin, and alkaline phosphatase values will be provided for each subject who met the criterion defined above.

For the **assessments of hepatic laboratory values** and **hepatic laboratory abnormalities of potential interest**, the maximum ratio relative to the ULN will be used to determine if subjects meet any of the criteria listed above. The ALT and total bilirubin values do not need to be concurrent in order to meet the defined criteria in statistical summaries. For ALT, the post-baseline value must represent an increase from the first nadir (including baseline) to be counted. First nadir is defined as the last value prior to the first increase. For total bilirubin, a subject will be counted if the post-baseline laboratory value meets the above criteria regardless of the baseline laboratory value (i.e., the post-baseline laboratory value does not need to be worse than the baseline laboratory value), except where noted above. A confirmed post-nadir increase in ALT is defined as two consecutive values of ALT  $> 5 \times$  ULN after nadir, either both during treatment or at the final treatment measurement and the next consecutive post-treatment measurement. A single post-nadir ALT value of greater than  $5 \times$  ULN followed by lost to follow-up (no additional ALT values) also will be considered (i.e., will not require confirmation). The ratio of direct to total bilirubin will be calculated using the same date/time sample corresponding to the total bilirubin elevation.

## 11.4 Analysis of Vital Signs and Weight

### 11.4.1 Variables and Criteria Defining Abnormality

Vital sign variables are body temperature, sitting systolic blood pressure, sitting diastolic blood pressure, sitting pulse rate, and body weight.

The criteria for potentially clinically significant (PCS) vital sign findings are presented in [Table 11](#).

**Table 11. Criteria for Potentially Clinically Significant Vital Sign Values**

Test/Measurement	Very Low (VL)	Very High (VH)
Systolic Blood Pressure	$\leq 90$ mmHg AND A decrease of $\geq 20$ mmHg from baseline	$\geq 180$ mmHg AND An increase of $\geq 20$ mmHg from baseline
Diastolic Blood Pressure	$\leq 50$ mmHg AND A decrease of $\geq 15$ mmHg from baseline	$\geq 105$ mmHg AND An increase of $\geq 15$ mmHg from baseline
Pulse Rate	$\leq 50$ bpm AND A decrease of $\geq 15$ bpm from baseline	$\geq 120$ bpm AND An increase of $\geq 15$ bpm from baseline
Weight	A decrease of $\geq 15\%$ from baseline	An increase of $\geq 15\%$ from baseline
Body Temperature		$> 38.3^{\circ}\text{C}$ AND An increase of $\geq 1.1^{\circ}\text{C}$ from baseline

### 11.4.2 Statistical Methods

The baseline value for vital signs will be the last measurement on or before the day of the first dose of study drug. The same baseline value will be used for changes at Treatment Period visits and changes at Post-Treatment Period visits.

Changes from baseline to each post-baseline visit, including applicable post-treatment visits, will be summarized. Each vital sign parameter will be summarized with the baseline mean; visit mean; and change from baseline mean, standard deviation, minimum, median, and maximum.

The number and percentage of subjects with on-treatment values meeting the specified criteria for PCS vital sign values (Table 11) will be summarized. A post-baseline value must be more extreme than the baseline value to be considered a PCS finding. A separate listing will be provided that presents all vital sign values for the subjects meeting PCS criteria during treatment.

### **11.5 Analysis of Child-Pugh Score**

For subjects with compensated cirrhosis, Child-Pugh scores will be categorized as 5, 6, > 6, or missing at baseline and each protocol-specified post-baseline visit, including applicable post-treatment visits. Shift tables from baseline to each post-baseline visit will be created for the cirrhotic subjects in the safety population. The shift tables will cross-tabulate the frequency of subjects with baseline values in each category versus the post-baseline categories. For each baseline category and across the baseline categories, the percentage of subjects in each post-baseline category (excluding the post-baseline category of missing) will be calculated.

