## 4.2 Design Diagram

This is a Phase 3b, open-label, non-randomized, multicenter study to evaluate the efficacy and safety of GLE/PIB for 8, 12, or 16 weeks in HCV GT1 – 6-infected subjects with chronic renal impairment, with compensated cirrhosis or without cirrhosis, who are either HCV TN or prior TE with interferon [IFN] or pegylated IFN [pegIFN] with or without RBV, or sofosbuvir [SOF] plus RBV with or without pegIFN. This study will consist of a Screening Period, a Treatment Period, and a Post-Treatment Period. A study schematic is shown below in [Figure 1](#).

[figure not shown]
The study is designed to enroll approximately 120 eligible subjects. The study enrollment will be monitored to meet the following non-mutually exclusive enrollment criteria: (1) up to approximately 40 subjects with Stage 3b CKD, (2) up to approximately 75 HCV GT1-infected subjects, (3) up to approximately 30 subjects with compensated cirrhosis.

Subjects will be enrolled into one of the following treatment arms:

- Arm A: HCV GT1, 2, 4 – 6 subjects without cirrhosis who are TN or TE and HCV GT 3 subjects without cirrhosis who are TN will be treated for 8 weeks.
- Arm B: HCV GT1, 2, 4 – 6 subjects with compensated cirrhosis who are TN or TE and HCV GT 3 subjects with compensated cirrhosis who are TN will be treated for 12 weeks.
- Arm C: All HCV GT3 subjects who are TE will be treated for 16 weeks.

Subjects with mixed HCV genotype infection should receive whichever duration is longer based on their genotypes, cirrhosis status, and treatment experience. For subjects with an indeterminate genotype, treatment duration will default to the respective GT3 duration based upon treatment-experience and cirrhosis status.

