### **7.1 Demographic and Baseline Characteristics**

Categorical demographic and baseline characteristic variables will be summarized with the number and percentage of subjects in each category. Continuous variables will be summarized with descriptive statistics (number of non-missing observations, mean, standard deviation, median, maximum and minimum). For categorical variables, the number of missing observations will be displayed, if applicable, on the summary tables. Percentages will be calculated based on the number of non-missing observations.

Continuous demographic and baseline characteristics include age, weight, height, body mass index (BMI), baseline  $\log_{10}$  HCV RNA level, creatinine clearance (Cockcroft-Gault calculation), eGFR (using the modification of diet in renal disease [MDRD] formula), platelet count, albumin, GGT, APRI, FIB-4, AST, ALT, and total, direct and indirect bilirubin.

Categorical demographic and baseline characteristics include:

- Age (< 65 or  $\geq$  65 years) and (< 75 or  $\geq$  75 years);
- Sex (male or female);
- Race and black race: black or non-black;
- Ethnicity (Hispanic or Latino, Not Hispanic or Latino);
- Geographic region (North America, Europe, or rest of world);

- Country;
- Baseline BMI ( $< 30$  or  $\geq 30$  kg/m^2);
- HCV genotype and subtype (using central laboratory results and final genotype/subtype results, see Section 10.8);
- Prior HCV treatment history (naïve or experienced);
- For treatment-experienced subjects, type of previous regimen (IFN- or SOF-based);
- Baseline cirrhosis status (yes/no);
- For cirrhotic subjects, Baseline Child-Pugh score (5, 6, or  $> 6$ );
- Chronic Kidney Disease stage at screening (Stage 3b, Stage 4, Stage 5 without dialysis, or Stage 5 requiring dialysis);
- For treatment-experienced subjects, type of non-response to previous treatment (on-treatment non-responder, breakthrough, post-treatment relapse, or unknown/other);
- Baseline HCV RNA level ( $< 1,000,000$ ;  $\geq 1,000,000$  to  $< 2,000,000$ ; or  $\geq 2,000,000$  IU/mL);
- Baseline platelet count ( $< 90$  or  $\geq 90 \times 10^9/L$ );
- Baseline albumin ( $< 35$  or  $\geq 35$  g/L);
- Baseline eGFR ( $< 15$ ,  $\geq 15$  to  $< 30$ ,  $\geq 30$  to  $< 45$ , or  $\geq 45$  mL/min/1.73 m^2);
- Baseline creatinine clearance ( $< 15$ , or  $\geq 15$  mL/min);
- Baseline fibrosis stage (equivalent to Metavir F0 – F1, F2, F3, or F4);

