**Table 5. Baseline Fibrosis Stage**

Baseline Fibrosis Stage, Metavir Equivalents	Liver Biopsy Metavir, Batts Ludwig, Knodell, IASL, Scheuer, or Laennec Score	Liver Biopsy Ishak Score	FibroScan (kPa)	FibroTest*
F0 – F1	0 or 1	0, 1, or 2	< 8.8	≤ 0.48
F2	2	3	≥ 8.8 to < 9.6	0.49 to 0.58
F3	3	4	≥ 9.6 to < 12.5	0.59 to 0.74
F4	4	≥ 5	≥ 12.5	≥ 0.75

\* APRI will not be used to derive baseline Fibrosis Stage. However, per inclusion/exclusion criteria, subjects need to have concordant FibroTest and APRI scores in order to determine eligibility.

The central laboratory calculates the estimated creatinine clearance (CrCl) based on the following Cockcroft-Gault formula:

$$\text{CrCl (mL/min)} = [(140 - \text{age}) \times (\text{weight in kg}) \times (0.85 \text{ if female})] / [(\text{serum creatinine (mg/dL)} \times 72)].$$

The central laboratory calculates the eGFR by MDRD based on the following formula:

$$\text{eGFR (mL/min/1.73 m}^2\text{)} = 175 \times (\text{Serum Creatinine})^{-1.154} \times (\text{Age})^{-0.203} \times (0.742 \text{ if female}) \times (1.212 \text{ if African American}).$$

Baseline APRI and FIB-4 are calculated by the equations below. Subjects who do not have concurrent AST and platelet values at baseline will be excluded from the summary of baseline APRI. Age is defined in years at baseline. Subjects who do not have concurrent values of AST, ALT and platelet count at baseline or subjects who are missing age will be excluded from the summary of FIB-4.

$$\text{APRI} = \frac{\frac{\text{AST Level (U/L)}}{\text{AST (Upper Limit of Normal)(U/L)}}}{\text{Platelet Count (10}^9\text{/L)}} \times 100$$

$$\text{FIB-4} = \frac{\text{Age (years)} \times \text{AST Level (U/L)}}{\text{Platelet Count (10}^9\text{/L)} \times \sqrt{\text{ALT (U/L)}}}$$

Presence or absence of cirrhosis will be determined as collected in IRT/EDC ("subject's cirrhosis status?" – "Compensated cirrhotic" or "Non-cirrhotic").

Baseline Child-Pugh score is determined by the Day 1 assessment of ascites and hepatic encephalopathy along with the baseline values of total bilirubin, serum albumin, and international normalized ratio (INR). The Child-Pugh score is the sum of the points assigned for each of the five observed findings as defined in [Table 6](#).

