**Table 6. Child-Pugh Classification of Severity of Cirrhosis**

Parameter	Points Assigned for Observed Findings		
	1	2	3
Total bilirubin, $\mu\text{mol/L}$ (mg/dL)	< 34.2 (< 2)	34.2 – 51.3 (2 – 3)	> 51.3 (> 3)
Serum albumin, g/L (g/dL)	> 35 (> 3.5)	28 – 35 (2.8 – 3.5)	< 28 (< 2.8)
INR	< 1.7	1.7 – 2.3	> 2.3
Ascites*	None	Slight	Moderate to severe
Hepatic encephalopathy**	None	Grade 1 or 2 (or suppressed with medication)	Grade 3 or 4 (or refractory to medication)

Child-Pugh category A: 5 – 6 points; Child-Pugh category B: 7 – 9 points; Child-Pugh category C: 10 – 15 points

\* None;

Slight ascites = Ascites detectable only by ultrasound examination;

Moderate ascites = Ascites manifested by moderate symmetrical distension of the abdomen;

Severe ascites = Large or gross ascites with marked abdominal distension.

\*\* None: normal consciousness, personality, neurological examination, electroencephalogram;

Grade 1: restless, sleep disturbed, irritable/agitated, tremor, impaired handwriting, 5 cps waves;

Grade 2: lethargic, time-disoriented, inappropriate behavior, asterixis, ataxia, slow triphasic waves;

Grade 3: somnolent, stuporous, place-disoriented, hyperactive reflexes, rigidity, slower waves;

Grade 4: unarousable coma, no personality/behavior, decerebrate, slow 2 to 3 cps delta activity.

Histories of diabetes, bleeding disorders, depression or bipolar disorder, hypertension, and cardiovascular disease will be based on the Medical/Surgical History eCRF, as defined in Table 7.

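### The Child-Pugh shift table groups scores 7 to 15 together, so it shows loss of category A but not whether a subject reached B or C, nor any rise from a baseline above 6

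*SAP*

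**What the plan says.** Section 11.5 covers subjects with compensated cirrhosis: "Child-Pugh scores will be categorized as 5, 6, > 6, or missing at baseline and each protocol-specified post-baseline visit". The output is a set of shift tables: "Shift tables from baseline to each post-baseline visit will be created for the cirrhotic subjects in the safety population", in which "The shift tables will cross-tabulate the frequency of subjects with baseline values in each category versus the post-baseline categories", with percentages. The section plans no summary of numeric change and no by-subject listing of scores.

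Section 7.1 uses the same three score groups (5, 6, above 6) for the baseline characteristic in cirrhotic subjects. The note to Table 6 gives the classes: "Child-Pugh category A: 5 – 6 points; Child-Pugh category B: 7 – 9 points; Child-Pugh category C: 10 – 15 points".

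Cirrhosis status and the score come from different sources. On status, section 7.1 says: "Presence or absence of cirrhosis will be determined as collected in IRT/EDC". The baseline score is derived from the Day 1 assessment of ascites and encephalopathy together with baseline bilirubin, albumin and INR. Section 4.2 limits this group to "up to approximately 30 subjects with compensated cirrhosis".

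**The concern.** The categories separate 5 from 6, which both lie in category A, but make no separation from 7 upwards, where Table 6 draws the line between B and C. This has two consequences.

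- For a subject who starts in category A, a one-point move to 7 and a move to 10 or more are counted in the same cell.
- For a subject labelled compensated whose derived baseline score is above 6, no later worsening can appear in the table.

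Safety is part of the primary objective in section 4.1, and the plan treats hepatic decompensation as an event of special interest. At stake is how much the report can say about the size of any hepatic deterioration in the cirrhotic subjects.

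**Working it through.** Section 11.5 states no figure to reproduce. The check maps every possible score to the planned categories and to the Table 6 classes, then asks what the other planned outputs would show.

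**1. Inputs.** Five components are scored 1 to 3 each (Table 6), so scores run from 5 to 15, which is 11 values. Planned categories: {5}, {6}, {7–15}. Table 6 classes: A = {5, 6}, B = {7, 8, 9}, C = {10–15}. The top category therefore holds 3 + 6 = 9 of the 11 values.

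**2. Starting in category A.** From 5 or 6, the three B scores and the six C scores all fall in the above-6 column. As an example at the low end, albumin of 36 g/L scores 1 point and 35 g/L scores 2. That change alone takes a subject from 6 to 7, and a subject going from 6 to 12 is counted in the same cell.

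**3. All possible worsenings.** Pairs with a later score higher than the baseline score: 11 × 10 / 2 = 55.

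| Type of worsening | Pairs | Changes category as planned | Changes category with 5, 6, 7–9, 10–15 |
|---|---|---|---|
| 5 to 6 | 1 | yes | yes |
| A to B or C | 2 × 9 = 18 | yes, but B and C share a cell | yes, B and C separate |
| B to C | 3 × 6 = 18 | no | yes |
| Within B | 3 × 2 / 2 = 3 | no | no |
| Within C | 6 × 5 / 2 = 15 | no | no |

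As planned, 18 + 3 + 15 = 36 of 55 pairs stay on the diagonal, and all of them start above 6. With the Table 6 classes, 3 + 15 = 18 remain there.

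**4. Size on the patient scale.** With 30 cirrhotic subjects, one subject is 1/30 = 3.3%. The SAP gives no frequency for category C or for baseline scores above 6, so no expected count can be derived.

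**5. What other outputs cover.**

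- Decompensation events are tabulated and listed only if treatment-emergent (section 11.2.3), meaning onset no later than 30 days after the last dose (section 11.2.1). In Table 3 the Post-Treatment Week 12 window opens on Study Drug End Day 57 and the Week 24 window on Day 127, both after that limit.
- The hepatic laboratory criteria apply during treatment, and the laboratory shift tables cover the Treatment Period (section 11.3.2).
- The note to Table 3 places post-treatment hematology, chemistry and coagulation panels at Post-Treatment Week 4 or at post-treatment discontinuation. It places Child-Pugh at Post-Treatment Weeks 12 and 24 (or discontinuation).
- The listing of all serious adverse events runs to the end of the study (section 11.2.4), but it carries no score.

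**The case against.** The strongest reply is that the cut at 6 suits the population. These subjects are enrolled as compensated, category A is 5 to 6, and a score above 6 is exactly the loss of category A. That stands: the main signal is visible, and for subjects who start in A only the size of the worsening is lost.

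The second reply is that severe progression would be seen elsewhere. Going from 6 or less to 10 or more takes at least 4 points. If ascites and encephalopathy do not worsen, three laboratory components must supply them, so at least one must rise by 2 points, from 1 to 3. For albumin that means falling from above 35 to below 28 g/L, which reaches grade 2 in Table 10 and triggers a listing. Bilirubin above 51.3 µmol/L or INR above 2.3 would normally be grade 2 as well (assuming a bilirubin ULN below about 34 µmol/L and an INR ULN below about 1.5). Worsening ascites or encephalopathy would be expected among the adverse events. This also largely stands for A to C during treatment. It does not carry over to subjects who start in B: a move from 9 to 10 through albumin falling from 28 to 27 g/L stays within grade 2. It is also weaker late in follow-up, for the reasons of timing shown above. One caution is that the score at Weeks 12 and 24 needs bilirubin, albumin and INR values whose source the SAP does not state. If they are collected then, the laboratory summaries may cover part of this gap.

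Third, a reader might infer that the SAP contradicts itself or expects baseline scores above 6. The documents support neither. Sections 7.1 and 11.5 use the same groups, nothing obliges the shift table to follow the Table 6 classes, and providing a category is not predicting that anyone will fall in it.

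**Conclusion.** The point holds as a weakness of reporting, of low weight. The planned table shows loss of category A. It cannot separate B from C, and it cannot show any rise from a baseline above 6 unless the score returns to 6 or below. The count of 36 of 55 describes possible pairs of scores and says nothing about how many subjects are affected; that number may be zero for the baseline part.

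It would go too far to say that the plan would miss decompensation, or that this table is the plan's designated check on it. Section 11.2.3 identifies those events by a MedDRA query, and section 11.5 does not link the score to them. Nor does the SAP label the diagonal cell as unchanged; a subject above 6 at both times is openly shown as such. The conclusion rests on the SAP as it stands, which specifies no numeric change and no Child-Pugh listing. The primary efficacy endpoint is not affected.

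**What to change.** In sections 11.5 and 7.1, replace the three score groups with 5, 6, 7–9 (B) and 10–15 (C), keeping missing as planned in 11.5. Add a by-subject listing of total and component Child-Pugh scores at all visits for any cirrhotic subject with a score above 6 at any visit, and flag those above 6 at baseline. The listing is needed because the 18 pairs within B or within C would still not show in the table. It also makes visible any subject recorded as compensated in IRT/EDC whose derived score falls outside category A.

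The cost is SAP wording, one more row and column in the shift table, one more baseline category and one listing, all from data already collected. The downside is sparse cells among at most about 30 cirrhotic subjects.
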